### **3.6 Early Withdrawal of Subjects**

- 3.6.1 Progressive Disease: Subjects who have clinical or radiologic evidence of progressive disease will undergo an evaluation to document the nature of the abnormality. If progressive cancer is diagnosed and further treatment planned, subjects will be considered off study and all efforts will be made to follow the patients for survival and toxicity data.
- 3.6.2 Principal Investigator Decision: Subjects may be withdrawn at any time during the study if the Principal Investigator believes it is in the subject's best interest to be withdrawn. In this event, the reasons for withdrawal will be documented.
- 3.6.3 Subject Participation: Refusal to continue treatment, follow-up, or comply with the protocol, or the withdrawal of consent. In this event, the reasons for withdrawal will be documented.
- 3.6.4 New information becomes available that warrants discontinuation of the protocol.

Once the subject is withdrawn from the study, the primary reason for withdrawing from the study must be clearly documented in the subject's records and on the CRF. The investigator will assess each subject for response at the time of withdrawal.

Every effort will be made to follow subjects off study for toxicity and survival. Survival will be followed for a minimum of five years by means of medical records and an annual phone call by a member of the research team to the subject if no medical records are available. Every effort will be made to follow patients for overall survival.

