## 4 Radiation Therapy

### 4.1 Dose fractionation and specification

- 4.1.1 For patients with Stage I Seminoma, radiation fractions will be administered once daily, for five fractions per week from Mondays through Fridays, as well as weekends when deemed clinically appropriate, with the exclusion of Hospital Holidays, for a planned 10 to 25 fractions delivered over two to four weeks. For patients with Stage IIA and IIB Seminoma, an additional boost of 5 fractions will be delivered over 5 days. The number of fractions administered will be dependent of the clinical stage of each study subject.
- 4.1.2 For Stage I Seminoma, patients will be treated to a total dose of 20.0 Gy (RBE) to 30.0 Gy (RBE) in 150 cGy (RBE) to 200 cGy (RBE) fractions to CTVpara-aortic for those being treated to

the para-aortic region alone or to CTVpara-aortic + pelvis for those being treated both to the para-aortic and pelvic regions. For patients with Stage IIA and IIB Seminoma, the target volume must include the both the para-aortic and pelvic regions and a nodal volume encompassing nodal disease (prescribed to an additional 9.0 Gy (RBE) to 10.0 Gy (RBE) in 180 cGy (RBE) to 200 cGy (RBE) fractions. The treatment field and total radiation dose will be at the discretion of the treating radiation oncologist, and dependent on the clinical risk factors of each study subject. The maximum dose should not exceed the prescription dose by more than 7% (inhomogeneity less than or equal to 7% in a volume of 1 cc of the review structures).

- 4.1.3 Treatment breaks, if necessary, should not exceed two treatment days. Treatment breaks exceeding two days will be considered a major protocol violation. Treatment breaks should only be allowed as a means for study participants to recover from severe acute toxicity and/or for intercurrent illness, or due to treatment machine or cyclotron maintenance. To avoid treatment breaks, a photon-based backup treatment plan may be delivered. Any treatment break or delay for other social or logistical reasons will be considered a protocol deviation. Photon-based backup treatment should not exceed 2 days or 10% of the intended dose of radiation, whichever is less. All incidents of treatment breaks and the reasons for any such breaks must be clearly indicated in the treatment record.

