#### 6.2.3

6.2.4 During Radiation Therapy: each patient will be assessed at least weekly during radiation therapy treatment. Each assessment will include a pertinent physical examination, performance status assessment (Appendix C), toxicity assessment (as per protocol section 6.2.5), laboratory evaluation to include complete blood count (optional), and quality of life assessment with EORTC QLQ-C30 (Appendix D), Testicular Cancer Patient Diary Card (Appendix E), and EuroQol EQ-5D (Appendix F).

6.2.5 Immediately Following Radiation Therapy: each patient will be assessed weekly for the first eight weeks following the completion of radiation therapy. Each assessment will include quality of life assessment with EORTC QLQ-C30 (Appendix D), Testicular Cancer Patient Diary Card (Appendix E), and EuroQol EQ-5D (Appendix F). At the discretion of the treating radiation oncologist, these weekly assessments may be performed in the physician clinic, via Internet-based surveys, via questionnaires from the patient home, or over the phone.

6.2.6 Toxicity Assessment: Patients will be treated and followed for a minimum of 90 days after the start of radiation treatment to determine safety (acute toxicity). The Common Toxicity Criteria v4.0 (Appendix A) [73] will be used to report acute adverse events that occur within 90 days of treatment initiation and late adverse events that occur after 90 days of protocol therapy initiation for up to 5 years.

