#### 7.1.2 Endpoints

- Acute Toxicity is defined as any Grade 3 or higher non-hematologic toxicity that occurs within 90 days following the start of proton therapy. NCI Common toxicity criteria (CTC Version 4.0) grades will be employed (Appendix A).
- Late Toxicity is defined as any Grade 3 or higher non-hematologic toxicity that occurs beyond 90 days following the start of proton therapy. NCI Common toxicity criteria (CTC Version 4.0) grades will be employed (Appendix A).
- Clinical Efficacy: Time to local failure will be defined as the time from the start of radiation therapy to local failure. Time to distant failure will be defined as the time from the start of radiation therapy to distant failure. Relapse-free survival will be defined from the time from the start of radiation therapy to any failure or death. Cause-specific survival will be defined from the time from the start of radiation therapy to death due to seminoma. Overall survival will be

defined from the time from the start of radiation therapy to death due to any cause or last patient follow-up. These outcomes will be summarized at the end of the phase II study.

- Quality of Life Measures: EORTC QLQ-C30, Testicular Cancer Patient Diary Card, and EuroQol EQ-5D will be evaluated at multiple times during and post-radiation. We hypothesize that compared to baseline, quality of life measures will worsen during and immediately post-radiation and will then gradually improve after radiation. These deficits are expected to be less than those seen for photon treated patients and the time course to return to baseline should be shortened. These outcomes will be summarized at the end of the phase II study.
- Moderate to Severe Lethargy will be scored on the Testicular Cancer Patient Diary Card (Appendix E). The rate of moderate to severe lethargy at week 3 will be evaluated. This outcome will be summarized at the end of the phase II study.

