#### 7.1.4 Statistical Analyses.

- Acute and Late Toxicity: All acute and late toxicities will be graded by CTC Version 4.0 and tabulated. Toxicity rates and 95% confidence intervals will be calculated.
- Analysis by Radiation Therapy Type: all subjects enrolled in this study will be followed and assessed for all endpoint analyses. However, a separate analysis may be performed for subjects who were treated with photon therapy as a portion of their planned course of radiation therapy.
- Moderate to Severe Lethargy: The 3-week rate and 95% CI will be computed. A one-sample one-sided chi-square test will be performed to test the null hypothesis that the lethargy rate is 35% (same as photon) versus the alternative hypothesis that the rate is reduced to 20%. Patients must have a minimum of 21 days of follow-up to be included. As a secondary analysis, the 3-week lethargy rate and 95% exact CI will be computed for each disease stage. A Fisher's exact test will be employed compare these rates, to determine whether lethargy rates significantly differ by disease stage.
- Clinical Efficacy: Time to local failure and time to distant failure will be estimated by the cumulative incidence method within a competing risks framework (competing risks are local failure, distant failure, death). Relapse-free survival, cause-specific survival, and overall survival will be estimated by the Kaplan-Meier method. Median values and 95% confidence intervals will be calculated.
- Quality of Life: Longitudinal quality of life measurements will be examined by plots of mean $\pm$  SD over time. Repeated measures ANOVA or linear mixed effects models (to assess the impact of fixed effects covariates), will be used to analyze the repeated observations. Piecewise linear models may be required to fit non-linear trends, as expected for the initial decline and then gradual increase in quality of life measures.

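### Section 3.6 does not say that the diary continues after a patient stops radiation, which conflicts with 7.1.4 and can cost the week-3 primary endpoint score

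*Combined protocol and SAP*

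**What the plan says.** **Withdrawal (Section 3.6).** Item 3.6.3 lists "Refusal to continue treatment, follow-up, or comply with the protocol, or the withdrawal of consent" as a ground for early withdrawal, and 3.6.2 adds withdrawal by decision of the investigator. The data to be sought afterwards are described as follows: "Every effort will be made to follow subjects off study for toxicity and survival". The diary card, the EORTC QLQ-C30 and the EQ-5D are not mentioned in 3.6.

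**Diary schedule (Sections 6.1 and 6.2).** The diary is due before treatment, weekly during radiation (6.2.4), and then under 6.2.5: "each patient will be assessed weekly for the first eight weeks following the completion of radiation therapy". No schedule is written for a course that is stopped early.

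**Primary endpoint (Sections 7.1.2, 7.1.4 and 7.2).** "Moderate to Severe Lethargy will be scored on the Testicular Cancer Patient Diary Card (Appendix E"), and the week-3 rate is tested against 35%. Of the analysis set, 7.1.4 says: "Patients must have a minimum of 21 days of follow-up to be included". Section 7.2 treats a missing week-3 diary as attrition, assumes at most 5% of it, and allows up to 59 enrolled to reach 56 evaluable.

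**The opposing statement (Section 7.1.4).** In the bullet on analysis by type of radiation, the plan says that "all subjects enrolled in this study will be followed and assessed for all endpoint analyses".

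**The concern.** Stopping radiation and leaving the study are different events. A patient can refuse further fractions and still be willing to fill in a one-page card. Section 3.6.3 gives both events the same status, and coordinators handling such a patient would look there first. It does not tell them to keep collecting the diary.

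The timing makes this matter. Stage I treatment is "for a planned 10 to 25 fractions delivered over two to four weeks" (4.1.1), with a further boost in Stage IIA and IIB, so week 3 falls during treatment or soon after it. A patient who stops before then has left the weekly on-treatment schedule and, read literally, never reaches the completion that starts the post-treatment schedule.

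If those who stop are more lethargic than those who continue, their absence lowers the observed lethargy rate. A lower rate is what the trial counts as success. The enrolment allowance in 7.2 restores the number of evaluable patients but not the missing scores.

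**Working it through.** **1. The texts side by side**

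| Section | What it implies for a patient who stops radiation before week 3 |
|---|---|
| 3.6.3 | Withdrawn from the study, the same status as withdrawn consent |
| 3.6, closing paragraph | Toxicity and survival sought; diary not named, but not forbidden |
| 6.2.4 and 6.2.5 | Diary tied to radiation being given or completed |
| 7.1.4, radiation-type bullet | Followed and assessed for all endpoint analyses |
| 7.1.4, lethargy bullet, and 7.2 | Not in the primary analysis without 21 days of follow-up; counted as attrition without a week-3 diary |

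The first three rows point toward losing the diary and the fourth toward keeping it. The documents do not say which governs.

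**2. The plan's own figures**

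Inputs from 7.1.4 and 7.2: null 35%, alternative 20%, one-sided 5%, power 80%, attrition 5%.

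n = [(1.645 × √(0.35 × 0.65) + 0.842 × √(0.20 × 0.80)) / 0.15]² = 55.87, so 56. Then 56 / 0.95 = 58.9, so 59. Both figures reproduce. Power at 56 is 80.1% by the normal approximation and 78.3% by exact binomial. The test succeeds at 13 or fewer of 56 (exact type I error 4.1%).

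**3. What informative loss could do**

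Assumption: 3 of 59 patients, the plan's whole attrition allowance, stop before week 3, have no diary, and are all lethargic.

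z = (x/n − 0.35) / √(0.35 × 0.65 / n), one-sided, no continuity correction. The standard error is 0.0637 at n = 56 and 0.0621 at n = 59.

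| Observed | p | With the 3 lost scores | p | Verdict changes? |
|---|---|---|---|---|
| 13/56 (23.2%) | 0.032 | 16/59 (27.1%) | 0.10 | yes |
| 12/56 (21.4%) | 0.017 | 15/59 (25.4%) | 0.062 | yes |
| 11/56 (19.6%) | 0.008 | 14/59 (23.7%) | 0.035 | no |

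At 14/56 (p = 0.058) the trial has already failed, so only 12 or 13 changes the verdict. With 2 lost, 13/57 (p = 0.027) becomes 15/59 (p = 0.062) and 14/57 (p = 0.049) becomes 16/59 (p = 0.10). By contrast, 12/57 becomes 14/59, still a success.

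**4. Effect on the false-success rate, same assumption**

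If 35% of all 59 are lethargic and the 3 lost all are, the rate among those observed is (0.35 × 59 − 3) / 56 = 17.65 / 56 = 31.5%. The binomial chance of 13 or fewer of 56 at that rate is 11.4%, against 4.1% with no such loss.

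**5. Effect of the fix on sample size**

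None: 56 evaluable and 59 enrolled stand. If all 59 give a week-3 diary, the test succeeds at 14 or fewer of 59, with exact type I error 4.4% and exact power 81.2%.

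**The case against.** A reader might infer that the plan collects only toxicity and survival after withdrawal, so that the diary is certainly lost. The text does not go that far. Section 3.6 does not restrict collection to those two items, and 7.1.4, read as a general commitment, already requires the week-3 score. Section 6.2.1 also says that all subjects are evaluated weekly. Completion of radiation in 6.2.5 may simply mean the end of treatment, however reached. This stands: the documents conflict and do not settle the loss. It does not dispose of the point, because the sentence in 7.1.4 sits in a bullet on photon backup treatment, gives no diary schedule after stopping, and does not override 3.6.

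A reader might also object to the requirement that "The investigator will assess each subject for response at the time of withdrawal", on the ground that Stage I patients have no lesion to assess after orchiectomy. That is not part of this point. Stage IIA and IIB patients have nodal disease in which response can be assessed, and the requirement has no bearing on the diary.

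The numerical example is a chosen boundary case. At the design alternative, about 11 of 56, three lost lethargic patients would not change the result. Early stopping may also be rare: Section 1.1 calls acute toxicities generally mild and self-limiting, Sections 4.1.3 and 4.5 provide for treatment breaks, and a 10-fraction course is over by about two weeks. All of this stands as a limit on size.

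The 5% allowance in 7.2 is a fair answer to loss of power. It does not answer bias, because it assumes nothing about who is missing.

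**Conclusion.** The point holds as a conflict to be reconciled. Section 3.6 treats refusing further radiation as leaving the study and does not name the diary among the data still sought, while 7.1.4 says that everyone is followed for all endpoints. Followed as written, 3.6 can lose the primary endpoint score of a patient who stops before week 3.

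Any bias toward success rests on two assumptions that the documents do not supply: how many patients stop early, and whether they are more often lethargic. In the worst case within the plan's own attrition allowance, an observed 12 or 13 of 56 would be declared a success that the full 59 would not support, and the false-success rate at a true 35% would be 11.4% instead of 4.1%. Outside that narrow range of counts, or if stopping is unrelated to lethargy, the conclusion is not affected in this way. The change is still worth making before data are collected, because a missed week-3 score cannot be recovered later.

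**What to change.** Reconcile 3.6 with 7.1.4:

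- Separate three events in 3.6: stopping protocol radiation, stopping study visits, and withdrawing consent.
- State that a patient who only stops radiation, by his own choice or by investigator decision, continues the diary card, QLQ-C30 and EQ-5D on schedule, including week 3 counted from the first fraction, unless he declines or withdraws consent.
- Reword 6.2.5 so that the post-treatment series starts at completion or discontinuation of radiation therapy.
- Add a diary card at the time of withdrawal where the patient agrees.

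Leave unchanged the investigator's discretion under 3.6.2 to withdraw a subject. Nothing here bears on when or whether radiation is stopped; only data collection changes. After consent or authorization is withdrawn, 10.1.2 continues to govern what may be used or requested.

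The cost is protocol wording and a few more reminders and contacts for patients who have stopped treatment. Section 6.2.5 already allows completion online, at home or by phone, and the sample size does not change.

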### **3.7 Subject Data Collection**

All subject information obtained throughout this study will be entered directly into the Velos system at both the University of Pennsylvania and Massachusetts General Hospital using case report forms (CRFs). After the confirmation of eligibility the subject will be assigned a study specific number and be entered into the Velos system. Adverse Events (AEs) and Serious Adverse Events (SAEs) at each site will be entered into the Velos system within two weeks.

#### **3.7.1 Vision Tree Assessments**

Subjects will be completing Quality of Life forms using Vision Tree, Inc.. VisionTree Software, Inc, will enable patients to fill out their QOL forms from any location that has a computer with internet access. VisionTree has

Version: MAY 2014

developed a new tool, VisionTree Optimal Care (VTOC), a HIPAA-secure, user-friendly, web-based software system. The VTOC tool contains a Web-based system for global patient and trial administration access, which allows improved compliance and accuracy of data collection, validation, and reporting. It is compliant with the Title 21, *Code of Federal Regulations*, Part 11 statistical process control system, and provides a mobile solution for clinical trials. Outcomes data is collected with Microsoft Excel and PDF export of reports. VTOC also has mobile messaging and e-mail reminders. (See <http://www.visiontree.com> for details).

If patients decide to utilize VisionTree software in their participation in this study, they must have an e-mail address that they consent to use for this purpose. Patients' e-mail addresses are necessary for this study so that e-mail reminders may be sent to them to remind them to fill out QOL forms that are due. Patients who are interested in participating but do not yet have an e-mail address can obtain one for free from a number of sources (e.g., Yahoo!, Hotmail, or AOL) and thus, can still participate. The patient's e-mail address will be used for password-protected access to VTOC. Patients can complete the QOL forms anywhere with a secure login. Patients will receive a login card (either printed or sent via email) with which to log in using the secure, web-based VTOC portal. VTOC meets all HIPAA guidelines and is encrypted (via 128-bit SSL) for the security, privacy, and confidentiality of QOL information. It is similar to the secure login commonly used when performing on-line banking. The login card may be kept and maintained by the patient. Patients will be permitted to use paper versions of the forms if they experience difficulty using the Vision Tree website.

The patient's e-mail address will only be used for this study. Patients will only be sent e-mail reminders when QOL forms are due. A typical e-mail reminder would read: "Your Quality of Life forms for your study, "Proton Seminoma", are now due. Please go to <http://www....> to use your secure login to log in to your portal and complete the on-line forms. If any questions make you feel uncomfortable, you may skip those questions and not give an answer. If you have any questions, please e-mail or call your research coordinator at -UPenn coordinator's email or at MGH coordinator's email (for MGH patients). Thank you for participating in this study." The reminders will be created and placed into a study template that will be sent to patients at customized intervals. The first reminder will be sent at the beginning of the "window" to complete a QOL form, with a second reminder halfway through the window period if the QOL forms are not yet completed at that time. A maximum of 3 reminders will be sent for each time point; after a patient has completed all forms in the portal, a dialogue box will appear that says "Thank you for completing your Quality of Life forms," and the patient will no longer receive any remaining notices for that time point. The site research associate or study administrator will be informed through the VTOC "At-A-Glance" form management system when QOL forms have been completed.

## 4 Radiation Therapy

### 4.1 Dose fractionation and specification

- 4.1.1 For patients with Stage I Seminoma, radiation fractions will be administered once daily, for five fractions per week from Mondays through Fridays, as well as weekends when deemed clinically appropriate, with the exclusion of Hospital Holidays, for a planned 10 to 25 fractions delivered over two to four weeks. For patients with Stage IIA and IIB Seminoma, an additional boost of 5 fractions will be delivered over 5 days. The number of fractions administered will be dependent of the clinical stage of each study subject.
- 4.1.2 For Stage I Seminoma, patients will be treated to a total dose of 20.0 Gy (RBE) to 30.0 Gy (RBE) in 150 cGy (RBE) to 200 cGy (RBE) fractions to CTVpara-aortic for those being treated to

the para-aortic region alone or to CTVpara-aortic + pelvis for those being treated both to the para-aortic and pelvic regions. For patients with Stage IIA and IIB Seminoma, the target volume must include the both the para-aortic and pelvic regions and a nodal volume encompassing nodal disease (prescribed to an additional 9.0 Gy (RBE) to 10.0 Gy (RBE) in 180 cGy (RBE) to 200 cGy (RBE) fractions. The treatment field and total radiation dose will be at the discretion of the treating radiation oncologist, and dependent on the clinical risk factors of each study subject. The maximum dose should not exceed the prescription dose by more than 7% (inhomogeneity less than or equal to 7% in a volume of 1 cc of the review structures).

- 4.1.3 Treatment breaks, if necessary, should not exceed two treatment days. Treatment breaks exceeding two days will be considered a major protocol violation. Treatment breaks should only be allowed as a means for study participants to recover from severe acute toxicity and/or for intercurrent illness, or due to treatment machine or cyclotron maintenance. To avoid treatment breaks, a photon-based backup treatment plan may be delivered. Any treatment break or delay for other social or logistical reasons will be considered a protocol deviation. Photon-based backup treatment should not exceed 2 days or 10% of the intended dose of radiation, whichever is less. All incidents of treatment breaks and the reasons for any such breaks must be clearly indicated in the treatment record.

